2.0 INTRODUCTION

Total Knee Replacement (TKR) has evolved to a point where implant design combined with instrumentation and surgeon skill results in excellent implant survival. The New Zealand National Joint Register reported over 6000 knee replacements performed in New Zealand in 2009, with annual figures increasing over the last 10 years.

Total Knee Replacements are undertaken to treat a range of conditions including osteoarthritis, rheumatoid arthritis, avascular necrosis and secondary arthritis resulting from trauma.

Current surgical techniques make use of generic, re-usable instrumentation, consisting of intra- and/or extra-medullary rods on the femur and tibia to determine alignment in relation to anatomical landmarks, combined with bone resection guides

which ultimately determine position and orientation of the definitive implant components.

Traditionally, the goal of TKR has been to position the components such that the post-operative alignment goal is a straight limb, or a mechanical axis of 0° (Insall & Scott, 2001). The mechanical axis is defined by lines joining the centre of the femoral head, centre of the knee joint and the centre of the ankle. Despite the best efforts of the surgeon, the resulting limb alignment varies away from 0° by a small amount (typically less than ±3° in 80% of cases).

More recently, the use of computer navigation systems has been introduced to surgical practice with the aim of improving the ability to obtain post-operative limb alignment as close as possible to 0° (Chauhan et al, 2004).

Whilst achievement of neutral limb alignment has been considered desirable from an engineering point-of-view – to maximize implant longevity through minimizing the deleterious effects of polyethylene insert wear and particle-induced osteolysis and implant loosening – patient satisfaction of TKR has not always been ideal. Despite surgery being performed technically correct by surgeons, up to 1 in 5 patients express dissatisfaction in the functional result (Bourne et al, 2009). Patient expectations after surgery are also increasing due in part to the adoption of more active lifestyles amongst total knee replacement recipients where return to function can be of primary importance.

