6.1 Inclusion Criteria

- The patient is a male or non-pregnant female between the ages of 40-80 years.
- The patient requires a primary total knee replacement and is indicated for computer-assisted surgery.

- Patient is deemed appropriate for a cruciate retaining knee replacement.
- The patient has a primary diagnosis of osteoarthritis (OA).
- The patient has intact collateral ligaments.
- The patient is able to undergo MRI scanning of the affected limb.
- The patient has signed the study specific, ethics-approved, Informed Consent document.
- The patient is willing and able to comply with the specified pre-operative and post-operative clinical and radiographic evaluations.

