6.2 Exclusion Criteria

- The patient has a history of total, unicompartmental reconstruction or fusion of the affected joint.
- Patient has had a previous osteotomy around the knee.
- The patient is morbidly obese (BMI ≥ 40).
- The patient has a deformity which will require the use of stems, wedges or augments in conjunction with the Triathlon Total Knee System.
- The patient has a varus/valgus malalignment ≥ 15° (relative to mechanical axis).
- The patient has a fixed flexion deformity ≥ 15°.
- The patient has a neuromuscular or neurosensory deficiency, which would limit the ability to assess the performance of the device.
- The patient has a systemic or metabolic disorder leading to progressive bone deterioration.
- The patient is immunologically suppressed or receiving steroids in excess of normal physiological requirements.
- Patient has a cognitive impairment, an intellectual disability or a mental illness.
- The patient is pregnant.
- The patient has metal hardware present in the region of the hip, knee or ankle (as this is known to create geometrical distortion in the region of the implant).
- The patient has any known contraindications for undergoing assessment by MRI (e.g. ferrous implants, metallic clips, magnetically activated implanted devices such as cardiac pacemakers, etc.).

6.3 Extension Study: Inclusion Criteria (applicable to patients electing to continue participation in the Extension Study)

- Patient was enrolled in ShapeNZRCT-10 and completed either the 6 month or 12 month follow-up visit (or both).
- Patient is willing and able to give informed consent to participate in the study.
- Patient is willing and able to comply with the specified clinical and radiographic evaluations.

6.4Extension Study: Exclusion Criteria (applicable to patients electing to continue participation in the Extension Study)

- Patient no longer has the Triathlon[®] Total Knee System in situ, including patients that have had revision surgery.
- Patient has a cognitive impairment, an intellectual disability or a mental illness that is considered by the investigator to inhibit the patient's capacity to consent to research and the ability to participate in it.
- Patient no longer resides in a geographical location that would reasonably permit clinic visits at protocol specified intervals.

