12.2 Data Capture and Analysis

All data will be recorded on 2-part NCR paper Case Report Forms (CRFs). The surgeon will complete and sign forms at the time of completion. Original CRFs will be collected by Stryker for data entry. Copies will remain at the Investigator site. Archiving will be undertaken in accordance with ICH/GCP guidelines (Appendix 6).

Any unclear or ambiguous data will be queried and all cleaned data will be entered into a database for tracking purposes.

The primary outcome data gathered from patients in each study group will be pooled and summarized.

For the primary objective of the study, the 95% confidence interval of the difference in total Oxford Knee Score improvement (at 12 months post-operative) between the Intervention Group and the Control Group will be computed. Two and five year data will be analysed as per the 12 month data.

For secondary objectives, independent two-sample t-test or Wilcoxon non-parametric rank-sum test will be used to compare the International Knee Society Score (IKSS), Forgotten Joint Score (FJS), WOMAC, EQ-5D and VAS Pain scores between the Intervention Group and the Control Group at all available visits. Please note that the test we intend on using will be dependent on the distribution of the data collected following appropriate normality testing. Adjustments will be made for multiple testing at each level.

Independent two-sample t-test or Wilcoxon non-parametric rank-sum test will also be used to compare cost-effectiveness and cost-utility between the Intervention Group and the Control Group. As mentioned above, this will also be dependent on the distribution of the data collected.

Adverse events will be tabulated separately and reviewed for any commonalities. Revision surgery data from the Extension Study will be compared to the revision rates reported in the National Joint Registry report at 2 years and 5 years. A cost benefit analysis will be undertaken with the use of data from the Australian Government Hospital Casemix Protocol Annual Report.

A formal interim analysis will take place following completion of the ShapeNZRCT-10 study (12 month visit). Additionally, formal interim analyses will take place following all participants' completion of the 2 year visit and again following completion of all participants' 5 year follow-up visits.

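### Section 12.2 compares extension revision data with registry rates not restricted to comparable patients, so a difference in either direction cannot be attributed to the device or technique

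*Combined protocol and SAP*

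**What the plan says.** Determining the revision rate is a secondary objective of the Extension Study (section 3.0). The analysis is one sentence in section 12.2: "Revision surgery data from the Extension Study will be compared to the revision rates reported in the National Joint Registry report", at 2 and 5 years. No section names a registry table or subgroup, a method of matching or standardisation, an interval, or a rule for interpreting the result. No comparison of revision between the randomised arms is stated.

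The trial population is narrow. Section 6.1 requires a primary diagnosis of osteoarthritis and a "male or non-pregnant female between the ages of 40-80 years". Section 6.2 excludes BMI of 40 or more, varus/valgus malalignment or fixed flexion of 15° or more, and earlier total or unicompartmental reconstruction. It also lists as an exclusion: "Patient has had a previous osteotomy around the knee". Section 8.1 specifies one cemented cruciate-retaining system for both arms.

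On the other side, section 2.0 cites the national register for over 6000 knee replacements in 2009 and says, of the operation in general: "Total Knee Replacements are undertaken to treat a range of conditions including osteoarthritis, rheumatoid arthritis, avascular necrosis and secondary arthritis resulting from trauma". Section 12.1 describes the registry's Oxford Knee Score data as coming mostly from conventional instruments.

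Three further provisions bear on which revisions are counted. Section 6.4 bars patients who have already been revised from the extension. Section 17.2 lists re-operation of the knee, including revision, as a reason for not continuing. Section 17.3 terminates unblinded patients and gives revision as an example of when unblinding may be needed.

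**The concern.** An external comparator is informative only if its patients would be expected to have the same event rate as the trial's patients. If the registry figure covers all knee replacements, a difference from the trial mixes patient selection, implant choice and surgical technique, and the plan has no step to separate them. A trial rate below the registry's could be reported as good survival of the technique, and one above it as a warning, when either could come from case mix alone.

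With at most 100 patients and few expected events, chance adds to this. Because no stratum is named in advance, the comparator could also be chosen after the revisions are known.

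A second problem lies in the numerator. If revisions before extension entry are left out while the registry counts from surgery (an assumption), the trial rate is too low whichever stratum is used.

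**Working it through.** **Plan's own figure.** There is none for revision. The only sample size is for the Oxford Knee Score: a 5-point difference, SD 8.30, 80% power, 5% significance. The normal formula gives 2 × (1.96 + 0.8416)² × 8.3² / 5² = 43.3, so 44. The t-based solution is 44.24, so 45, as stated, and 45 / 0.9 = 50. That calculation does not address revision.

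**Inputs for revision.** From the documents: at most 100 extension patients, 50 randomised per arm. Not in the documents, so assumed: the share s of registry knees outside the trial criteria (10-30%), their revision risk RR relative to eligible knees (0.7-3), the registry's cumulative revision rate (2-5%), and the share f of revisions that fall before extension entry (20-50%).

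**Case mix.** If eligible knees have risk p, the overall registry rate is p × (1 − s + s × RR). With no device effect, the expected trial-to-registry ratio is 1 / (1 − s + s × RR):

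| s | RR 0.7 | RR 1 | RR 1.5 | RR 2 | RR 3 |
|---|---|---|---|---|---|
| 10% | 1.031 | 1.000 | 0.952 | 0.909 | 0.833 |
| 20% | 1.064 | 1.000 | 0.909 | 0.833 | 0.714 |
| 30% | 1.099 | 1.000 | 0.870 | 0.769 | 0.625 |

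The extremes are 1 / (0.7 + 0.3 × 0.7) = 1 / 0.91 = 1.099 and 1 / (0.7 + 0.3 × 3) = 1 / 1.6 = 0.625. The range crosses 1.

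**Precision.** For zero events the exact two-sided 95% upper limit is 1 − 0.025^(1/n): 3.6% for n = 100 and 7.1% for n = 50. The exact interval is 0.6% to 8.5% for 3/100 and 0.05% to 10.7% for 1/50. These are best cases, since they assume that every patient joins and is followed completely.

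**Chance of falling below the registry rate.** Binomial, n = 100, probability that the observed rate is below the assumed registry rate:

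| Registry rate | Ratio 1.10 | Ratio 1 | Ratio 0.75 |
|---|---|---|---|
| 2% | 35% | 40% | 56% |
| 3% | 36% | 42% | 61% |
| 5% | 35% | 44% | 68% |

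With identical risk, the trial still falls below the registry about four times in ten.

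**Revisions before extension entry.** If a share f of revisions at cumulative rate p falls before entry and those patients cannot enter, the rate among entrants is p(1 − f) / (1 − pf). For p = 3%: 0.024 / 0.994 = 2.4% at f = 20%, and 0.015 / 0.985 = 1.5% at f = 50%. For p = 5%: 0.040 / 0.990 = 4.0% and 0.025 / 0.975 = 2.6%. The revision that ends participation can itself still be recorded. What can be lost is a revision before entry (section 6.4), or one that follows an earlier re-operation or unblinding after which the patient has left (sections 17.2 and 17.3).

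**The case against.** The best reply is that the plan is silent rather than wrong. Section 12.2 refers to reported rates in the plural and does not say that the all-patient rate will be used; the registry report may contain suitable breakdowns. No hypothesis, margin or survival claim is attached, so the comparison may be meant as description. First-year revisions should also be on record in the main study's adverse event data.

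Much of this stands. A reader might infer that the registry demonstrably includes patients the trial excludes, and that the trial will therefore look better. The documents do not support that. Registry case mix is inferred by joining two separate statements in section 2.0, a national count and a general list of indications. No revision rate by diagnosis, age, BMI, deformity or implant appears anywhere. The age limits alone could move the rate either way, and if the excluded patients had lower risk the trial would look worse.

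What the reply does not remove is that no comparator is fixed in advance, that the comparison is not called descriptive, and that the text specifies Extension Study data, which by section 6.4 cannot include patients revised before entry. A descriptive comparison still needs a comparable denominator and the same starting point for follow-up.

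**Conclusion.** The concern holds as a minor one. The registry comparator is not restricted to patients like those in the trial, and the resulting bias has neither an established direction nor an established size. On the assumed values, case mix alone gives an expected trial-to-registry ratio between about 1.10 and 0.625, and 0 revisions in 100 is compatible with a true rate of up to 3.6%. A conclusion that the plan is biased in the trial's favour through case mix would go beyond the documents.

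The loss of revisions before extension entry does have a direction, towards a lower trial rate, provided that registry rates count from surgery. Sections 6.4 and 17.2 must be reconciled with the revision objective in section 3.0. Neither issue affects the primary Oxford Knee Score analysis.

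**What to change.** Amend section 12.2 as follows:

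- Before the 2-year analysis, name the registry table and the closest stratum available: primary osteoarthritis, nearest age band, and the same implant where reported.
- Count revisions from surgery in all randomised patients, including those before extension entry. Patients who do not join the extension contribute up to their last study contact, and expected revisions are calculated over the same follow-up.
- Show observed against expected revisions with an exact 95% interval at 2 and 5 years, overall and by randomised arm.
- State that the comparison is descriptive, that BMI, deformity and previous surgery remain unmatched, and that it supports no claim of lower or equal revision risk.
- Reconcile sections 6.4 and 17.2 with the revision objective, so that it is clear which revisions enter the analysis.

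The cost is a paragraph of text, a table, and possibly a data request to a registry the plan already uses. The stratum rate will be less precise than the overall rate and may look less favourable to the trial. How close the match can be depends on the breakdowns the registry provides, which the documents do not show.

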1.0 SUMMARY

This is a prospective, randomized, longitudinal study of the clinical outcomes of osteoarthritis patients treated by two different alignment philosophies for total knee replacement. Participants will be treated using the Stryker Triathlon® Total Knee System for Total Knee Arthroplasty (TKA) implanted using either Stryker OtisMed® ShapeMatch® Technology (intervention) or Stryker PrecisioN v4.0 Knee Navigation (control). Health status and functional outcome measures will be recorded to quantify functional status of subjects before surgery and at each follow-up interval. An economics analysis will also be conducted to compare costs associated with each technology platform.

There will be 2 sites (North Shore Hospital, Auckland and Waitakere Hospital, Waitakere), 1 Principal Investigator and 6 co-Investigators for this study. A maximum of 50 cases will be enrolled in each group, for a total of 100 patients. It is expected that participants will be recruited over a 6 month period. Total duration of the study is expected to be 1.5 years.

The study consists of two groups:

- 1. Intervention Group: Treatment by total knee replacement with a target lower limb alignment determined using pre-operative imaging and kinematic alignment, implemented using Stryker OtisMed® ShapeMatch® Technology:
- 2. Control Group: Treatment by total knee replacement with a target lower limb alignment equal to neutral Mechanical Axis, implemented using Stryker Knee Navigation.

Pre-operatively, all participants will be required to undergo medical imaging assessment using Magnetic Resonance Imaging (MRI) of the affected lower limb. These images will then be used to manufacture the patient-specific cutting guides for preparation of the bones prior to implantation of the total knee replacement.

All participants (control and intervention groups) will be requested to attend visits preoperatively and post-operatively at 6 weeks, 6 months and 12 months. At these visits participants will complete assessments relating to quality of life, pain and functional outcome. In addition, participants will have standard knee X-rays taken preoperatively and post-operatively. A post-operative CT scan will be obtained for all participants in order to assess implant position and orientation.

All devices used in this study have been registered with MedSafe NZ and are approved for sale and use in New Zealand.

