3.0 OBJECTIVES

The primary objective of this study is:

• To demonstrate, through calculation of Oxford Knee Score at 12 months postoperative, that total knee replacement (TKR) performed using the ShapeMatch® Cutting Guide provides improvement from preoperative levels of patient pain and function comparable to the improvement obtained with TKR performed using computer-assisted Navigation. Oxford Knee Scores will be calculated pre-operatively and at 6 weeks, 6 months and 12 months post-operatively.

The secondary objectives of this study are:

- The efficacy objective is to compare radiographic, pain, function and health-related quality of life (QOL) between the ShapeMatch® Cutting Guide group and the computer-assisted Navigation control group. This objective will be achieved by utilizing the following instruments pre-operatively and at the 6-week, 6-month and 12 month visits:
 - Perth CT protocol
 - AP and ML X-rays
 - Oxford Knee Score
 - The International Knee Society Score (IKSS)

- The Forgotten Joint Score (FJS-12)
- WOMAC
- EQ-5D-3L
- VAS Pain
- To compare the cost-effectiveness and cost-utility of the procedure between the ShapeMatch[®] Cutting Guide group and the computer-assisted Navigation control group. This objective will be assessed by recording and calculating the following parameters:
 - o Wound length
 - Total duration of operating procedure (anaesthetic time and skinto-skin incision time)
 - o Cost of consumable items used during operating procedure
 - Length of stay in hospital
 - o Quality-adjusted life-years (QALYs) from EQ-5D-3L

The hypothesis is that there is a statistically significant improvement in functional outcome 12 months following a primary Total Knee Replacement when kinematic limb alignment (using ShapeMatch® Cutting Guide) is used compared to that resulting from a goal of neutral mechanical axis alignment (using computer-assisted Navigation).

The Extension Study Primary Objective is:

To determine the clinical and radiographic outcomes at 2 years and 5 years post-surgery, in patients receiving a Stryker Triathlon[®] Total Knee System for Total Knee Arthroplasty (TKA) implanted using either Stryker OtisMed[®] ShapeMatch[®] Technology (intervention) or Stryker PrecisioN v4.0 Knee Navigation (control).

The Extension Study Secondary Objectives are:

 To determine the revision rate, device-related adverse events and reoperation rates.

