8.2 Device Supply

The ShapeMatch[®] cutting guides will be supplied by Stryker New Zealand Ltd.

All other devices used in this study are commercially available products which will be obtained via the usual ordering and payment process.

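### The cost-benefit analysis names an Australian report as its only external cost source for a trial in two New Zealand hospitals, and is not linked to the resource use the trial records per patient

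*Combined protocol and SAP*

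**What the plan says.** The trial is set wholly in New Zealand. Section 1.0 states: "There will be 2 sites (North Shore Hospital, Auckland and Waitakere Hospital, Waitakere". The same section gives the purpose of the economic work: "An economics analysis will also be conducted to compare costs associated with each technology platform".

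Section 3.0 lists the economic objective as "To compare the cost-effectiveness and cost-utility of the procedure". Its inputs include "Total duration of operating procedure" (anaesthetic and skin-to-skin), "Cost of consumable items used during operating procedure", "Length of stay in hospital", wound length and QALYs from the EQ-5D-3L. Section 11.0 adds counts of instruments sterilised and used in each case, and an assessment of how each platform affects hospital cost and efficiency.

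Section 12.2 treats the economics in two places. One paragraph compares cost-effectiveness and cost-utility between arms by t-test or rank-sum test, with no cost source named. A later paragraph, directly after a sentence on Extension Study revision data, says a "cost benefit analysis will be undertaken with the use of data from the Australian Government Hospital Casemix Protocol Annual Report". Cost-benefit is not among the objectives in 3.0.

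On supply, section 8.2 says the sponsor's New Zealand company will supply the ShapeMatch guides, and then: "All other devices used in this study are commercially available products which will be obtained via the usual ordering and payment process".

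**The concern.** A comparison of two technology platforms needs costs that can differ between arms and that apply where the patients were treated. The only external cost source in the plan comes from another country, and nothing ties the analysis that uses it to the trial's own resource data.

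Three things are at stake:

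- **Relevance.** Australian prices, from another currency and health system, need not describe the two study hospitals.
- **Ability to separate the arms.** Both arms have a primary total knee replacement with the same implant family (sections 8.1 and 9.0). A source that prices the admission as a whole may not register a difference in instrumentation.
- **Even treatment of the technology.** The guide is single-use and used only in the intervention arm. The navigation system is used only in the control arm. Pricing one and not the other shifts the result.

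**Working it through.** The plan states no cost figure, so there is none to reproduce. The check is a reading of the sections, followed by algebra with symbols for prices the documents do not give.

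**Step 1. What is recorded and what values it**

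| Item | Recorded under | Unit | Unit-cost source named |
|---|---|---|---|
| Anaesthetic and skin-to-skin time | 3.0 | time | none |
| Length of stay | 3.0 | days | none |
| Instruments sterilised and used | 11.0 | count | none |
| Consumables | 3.0 | cost | none stated |
| Cost-benefit inputs | 12.2 | not stated | Australian report |

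Time, days and counts become costs only once multiplied by a price, and the plan gives no local source for those prices. For the report itself, 12.2 gives no edition, price year, currency conversion or list of inputs, and the bibliography in 24.0 does not include it.

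**Step 2. If the report gives one average per admission type**

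This is an assumption. Let that average be A. The admission-cost difference, intervention minus control, is

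A − A = 0.

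If the average is weighted by stay at w per day, and mean stays are L_I and L_C, it is

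w × (L_I − L_C).

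Theatre time, instruments and consumables do not enter either expression.

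**Step 3. The difference built from recorded resources**

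Let T be theatre time, N instruments sterilised, L days in hospital and K consumables other than the arm-specific technology, each as an arm mean, with unit costs a, s and b. Let p be the guide price per case, m the cost of the pre-operative MRI and v the per-case cost of navigation and its instrumentation. Then

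D = a(T_I − T_C) + s(N_I − N_C) + b(L_I − L_C) + (K_I − K_C) + p + m − v.

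The MRI appears once because, in section 11.0, the images are used to make the guides and control patients are scanned to maintain blinding.

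**Step 4. What each omission does to D**

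- Guide unpriced: D − p. Over 50 intervention cases the total understated is 50 × p.
- MRI charged to both arms: the scans cancel, giving D − m.
- Navigation uncosted: D + v.
- All three together: D − p − m + v.

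The first two favour the intervention and the third favours the control. The documents give none of p, m or v, so the net direction cannot be determined from them.

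**The case against.** The strongest reply is that section 12.2 says only that the report's data will be used. It does not say that all costs come from it or that trial data are excluded. Because the sentence follows the one on revision surgery, the report might supply revision costs alone, or a few unit prices. The listed objective is cost-effectiveness and cost-utility, which has its own patient-level inputs and its own comparison, and that comparison does not mention the report. The guide is a single-use item that could naturally count as a consumable. Fully pricing the guide while ignoring navigation would bias the result against the intervention.

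Much of this stands. A reader might infer that the cost-benefit analysis takes all its costs from Australian averages that cannot tell the two techniques apart. The documents do not support that: they neither describe the report's contents nor give it sole use. A reader might also infer from 8.2 that the guides are free or will be left uncosted. The contrast in that section raises the question but does not answer it.

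The reply does not remove the point. Whichever inputs the report supplies, they are Australian, and no reason or conversion is given. The separate comparison avoids the report but has no stated prices for time, stay or instruments. The objection about uneven pricing is right, and the fix below treats both arms alike.

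**Conclusion.** The point holds in this form: section 12.2 names an Australian report as the only external cost source for the cost-benefit analysis of a New Zealand trial, does not link that analysis to the recorded per-patient resource data, and names no unit-cost source for the cost-effectiveness and cost-utility comparison.

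Its size is conditional. The zero admission-cost difference depends on the assumption of a flat average per admission type. The understatement of one guide price per intervention case depends on costs being taken from hospital purchases and on the guide not passing through them. Neither condition is established by the documents, and no monetary figure can be given.

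This is a secondary matter, worth correcting because better data are already being collected. The primary Oxford Knee Score comparison is unaffected.

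**What to change.** Amend 12.2 as follows:

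- Make the main cost analysis each patient's recorded resource use (anaesthetic and skin-to-skin time without counting the same minutes twice, instruments sterilised and used, consumables, length of stay) multiplied by unit costs from the two study hospitals, in New Zealand dollars for a stated price year. Use the same costs in the cost-effectiveness and cost-utility comparison.
- Value both arms' technology on the same basis: the ShapeMatch guide at its New Zealand commercial price however it was supplied, and the navigation system with its associated instrumentation as a cost per case.
- Charge the pre-operative MRI to the intervention only, since control patients have it for blinding.
- Keep the Australian report as a sensitivity analysis, stating the edition, the inputs taken and the currency conversion. State also what the cost-benefit analysis adds to the objectives in 3.0.

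The cost is a change of SAP wording, a unit-cost request to the two hospitals (including a per-case figure for navigation), a guide price from the sponsor and some analyst time. No new patient data are needed. The downside for the sponsor is that the intervention may look less favourable on cost.
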